2.6. Baseline

The baseline as defined in study 64041575RSV2004 will be used in the presentation of demographics and disease characteristics. A footnote will indicate that the data are used from study 64041575RSV2004.

3. INTERIM ANALYSIS

An unblinded interim analysis was to be performed when all subjects from the first season in Study 64041575RSV2004 who are enrolled in this LTFU study complete the 18-month follow-up assessment of this LTFU study. This interim analysis was to serve an evaluation of the need for an extension of the follow-up period. The interim analysis was not performed as the project was stopped and due to the limited sample size, an extension of the follow-up period was not deemed useful for the objectives of this trial.

4. SUBJECT INFORMATION

Subject information will be analyzed on the All Enrolled set, defined as the subjects that enrolled in the 64041575RSV2002 study (i.e., signed informed consent).

4.1. Demographics and Baseline Characteristics

In this study (where no treatment is given), treatment will be used in summaries, where the treatment of RSV2004 will be presented. All demographics and baseline characteristics will be summarized overall and by treatment group. Descriptive statistics and frequency distribution will be provided for respectively the continuous and categorical parameters below. These data will be taken for the All Enrolled set from the data of the 64041575RSV2004 study, and at the time of enrollment in that study (eg age reported here is the age at the time of the index event).

Demographic parameters [to be inherited from the 64041575RSV2004 study]:

- Sex (Male, Female)
- Race (White, Black or African American, Asian, American Indian or Alaska Native, Native Hawaiian or Other Pacific Islander). If multiple race categories are indicated, the Race is recorded as 'Multiple'.
- Ethnicity (Hispanic or Latino, Not Hispanic or Latino)
- Country
- Geographic region (based on country: North America [to include Puerto Rico], Europe, South America, Asia-Pacific)
- Region (Japan, non-Japan) Note: Japan region only includes subjects indicated as Japanese on the eCRF.
- Age (months)
- Age category [≥ 28 days to < 24 months, ≥ 24 to ≤ 36 months]
- Weight at baseline (kg)
- Height at baseline (cm)
- BMI at baseline (kg/m^2) = Weight at baseline (kg) / (Height at baseline (m))² (rounded to 1 decimal)
- Gestational age at birth (Weeks)
- Prenatal smoking by the mother (yes, no)
- Exposure to tobacco smoke at home (yes, no)
- Contact with other children (yes, no)
- Attending day care (yes, no)
- Breastfeeding (yes, no)

Baseline disease characteristics

- Wheezing associated with symptoms of acute respiratory infections (yes, no)
- Personal or family history of atopy/allergy (yes, no)

[to be inherited from the 64041575RSV2004 study]:

- Duration of RSV symptoms from onset till time of randomization (days)
- Duration of RSV symptoms from onset till time of randomization (days) categories (≤ 3 days; > 3 days to ≤ 5 days)
- Presence comorbid conditions (yes, no)
- Number of subjects with one of following comorbid conditions:
 - o prematurity at birth [subject's gestational age was < 37 weeks; for infants < 1 year old at randomization],
 - o bronchopulmonary dysplasia,
 - o congenital heart disease,
 - o other congenital diseases,
 - o Down syndrome,
 - o neuromuscular impairment, or
 - o cystic fibrosis
- Baseline RSV subtype (Type A, Type B, Type A+B)
- Receiving Supplemental Oxygen (yes, no)
- Reasons for hospitalization (PRESORS question 1)

4.2. Disposition Information

The number of subjects in the following disposition categories will be summarized throughout the study by treatment group and overall:

- Subjects who completed and discontinued the trial, with the reasons of discontinuation
- Subjects per analysis visit in the trial

4.3. Protocol Deviations

Only major protocol deviations will be defined in this trial. All major protocol deviations will be listed, including the deviations to the inclusion-exclusion criteria, and the violations to the prohibitions and restrictions, if any. A tabulation of the number and percentage of subjects per major protocol deviation will be provided.

4.4. Medications

Medications will be coded using the [World Health Organization Drug Dictionary (WHO-DD)] in the version current at database lock. Summaries of medications (number and percent of subjects) will be presented by treatment group.

4.5. Preplanned Surgeries/Procedures

A tabulation and listing of the preplanned surgeries/procedures requiring hospitalization will be made.

5. EFFICACY

5.1. Primary Efficacy Endpoint(s)

5.1.1. Definition

The primary endpoints are:

1. Clinical diagnosis of asthma within the first 2 years after the RSV infection, as diagnosed by a physician and reported by the parent/caregiver. This will be derived based on the completed study questionnaires at each visit/telephone call until the final visit. It is either “Yes” or “No”.
2. The percentage of wheezing days in a subject within the first 2 years after the RSV infection will be calculated as:

$$\text{Percentage of wheezing days} = \left(\frac{\text{number of wheezing days}}{\text{day of study completion} - \text{day of informed consent} + 1} \right) * 100$$

The percentage will be rounded to the nearest integer. Number of wheezing days is the sum of all days that were reported in the Monthly visit reports. The day of informed consent is the informed consent of the RSV2002 study.

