**TIME AND EVENTS SCHEDULE**

Study Period	Entry Visit a,b	Assessment Period b				
	Months	0	3 (±7 days)	6 (±7 days)	12 (±7 days)	18 (±7 days)
Screening/Administrative						
Informed consent	X					
Eligibility criteria	X					
Baseline demographics c	X					
Medical and family history c,d	X					
Wheezing and medication parent/caregiver card distribution and verification e,f	X	X	X	X	X	X
Clinical Evaluations						
Clinician questionnaire g	X	X	X	X	X	X
	Monthly telephone calls between study site visits h					
Collection of data from lung function tests and allergy tests (immunoglobulin E and skin tests) i			X			
Medical resource utilization j			X			
Medication l			X			
Safety Evaluations						
Serious/reportable adverse events k			X			

- a. The entry visit needs to take place within 3 months after randomization in Study 64041575RSV2004. The last visit of Study 64041575RSV2004 (ie, Day 28) may be used as the entry visit for this study.
- b. Assessments will be performed during study site visits (entry visit and 3, 6, 12, 18, and 24 months after entry visit in Study64041575RSV2002) and during monthly telephone calls with the parent/caregiver between study site visits.
- c. Baseline demographics and medical/family history from the previous Phase 2 Study 64041575RSV2004 will be captured in the long-term follow-up electronic case report form (eCRF).
- d. Medical and family history to identify risk factors for wheezing/asthma at baseline, including prenatal smoking by the subject's mother, subject's exposure to tobacco smoke, wheezing associated with symptoms of acute respiratory infections, whether the subject has siblings or attends kindergarten/day care, and personal and/or family history of atopy/allergy will be recorded in the eCRF.
- e. Parents/caregivers will be provided with a wheezing parent/caregiver card to be completed daily. The information recorded on the wheezing parent/caregiver card will aid the site responsible person to complete the clinical questionnaire when interviewing the subject's parent/caregiver. Parents/caregivers will be required to return the completed parent/caregiver cards to the study sites every 3 months (eg, in person or by mail/email/fax when no study site visit is scheduled).

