#### 9.1.2. Entry Visit

Screening can be performed as soon as it is confirmed that the subject participated in Study 64041575RSV2004 and completed the planned course of the study drug and the last study-related visit. Subjects may be enrolled within 3 months after randomization in Study 64041575RSV2004. The last visit of Study 64041575RSV2004 (ie, Day 28) may be combined with the entry visit of this LTFU study (Study 64041575RSV2002).

At the entry visit, after signing the ICF, the overall eligibility of the subject to participate in the study will be assessed.

Baseline demographics and medical/family history from the previous Phase 2 Study 64041575RSV2004 will be captured in the LTFU (Study 64041575RSV2002) eCRF. Medical and family history to identify risk factors for wheezing/asthma at baseline, including prenatal smoking by the subject's mother, subject's exposure to tobacco smoke, wheezing associated with symptoms of acute respiratory infections, whether the subject has siblings or attends kindergarten/day care, and personal and/or family history of atopy/allergy will be recorded in the eCRF.

Parents/caregivers will be provided with the medication and wheezing parent/caregiver cards, both of which need to be completed on a daily basis (see [Attachment 3](#) and [Attachment 4](#)).

During the entry visit, a clinical questionnaire (see [Attachment 2](#)) needs to be completed by a study site responsible person, by interviewing the subject's parent/caregiver, to collect the following information:

- Wheezing.
- Diagnosis of asthma, eczema, and allergic rhinitis. All medical information needed to confirm the diagnosis of asthma, eczema, and allergic rhinitis needs to be collected by the study site personnel.
- Impact of the subject's health status on normal daily activities for subjects, parents/caregivers, and other family members.

This questionnaire will capture information since the last study visit:

- If the entry visit of Study 64041575RSV2002 coincides with the last visit of Study 64041575RSV2004 (ie, Day 28), the "last study visit" in the questionnaire refers to

the Day 14 visit in Study 64041575RSV2004. Any recalled events in the questionnaire will be related to this time period.

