### **9.1.3. Study Period**

No study drug will be administered.

The medical follow-up of the subjects will be performed according to the local standard of care during the assessment period.

At each study site visit (3, 6, 12, 18, and 24 months after entry visit) as noted in the [Time and Events Schedule](#) and during a monthly telephone call (calendar month  $\pm 7$  days), a clinical questionnaire (see [Attachment 2](#)) will be completed by a study site responsible person, by interviewing the subject’s parent/caregiver, to collect the following information:

- Wheezing.  
The parent/caregiver will be provided with a wheezing parent/caregiver card to be completed daily (see [Attachment 3](#)) which will aid the site responsible person in completing the questionnaire.
- Diagnosis of asthma, eczema, and allergic rhinitis. All medical information needed to confirm the diagnosis of asthma, eczema, and allergic rhinitis needs to be collected by the study site personnel.
- Impact of the subject’s health status on normal daily activities for subjects, parents/caregivers, and other family members.

Medical resource utilization data will be collected throughout the study.

Parents/caregivers will also be provided with a medication parent/caregiver card to record medication use on a daily basis (see [Attachment 4](#)).

Parents/caregivers will be required to return the completed wheezing and medication parent/caregiver cards to the study sites every 3 months (eg, in person or by mail/email/fax when no study site visit is scheduled).

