1.2. Trial Design

This is a global, multicenter, blinded, LTFU study to evaluate the incidence of the clinical diagnosis of asthma and the frequency of wheezing in infants and children (otherwise healthy or with underlying comorbidities for severe RSV) who have completed their treatment course and their last study-related visit in a previous Phase 2 study, 64041575RSV2004, in which they received lumicitabine or placebo for the treatment of RSV infection. Subjects will be followed for at least 2 years following treatment. This study may be extended up to an additional 3 years (i.e., total duration up to 5 years after randomization into Study 64041575RSV2004). Participation in this LTFU study is optional for study sites. This LTFU study will be offered to subjects of Study 64041575RSV2004 if their site decides to participate in this LTFU study.

Subjects will be enrolled within 3 months after randomization in Study 64041575RSV2004.

No study drug will be administered in this study. The parent/caregiver of the subject and the investigator will remain blinded to the study treatment (lumicitabine or placebo) administered in Study 64041575RSV2004 until the completion of this LTFU study, including any extension period.

Assessments will be performed at the study site at enrollment in this study and at 3, 6, 12, 18, and 24 months after randomization in Study 64041575RSV2004. The last visit of Study 64041575RSV2004 may be combined with the entry visit of this LTFU study. The same assessments will be performed during monthly phone calls with the parent/caregiver between the study site visits.

More details can be found in the Time-and-Event schedule in the study protocol.

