5.1.3. Analysis Methods

The proportions of subjects with clinical diagnosis of asthma within the first 2 years after the RSV infection will be presented descriptively by previous treatment group, together with the 95% (2-sided) confidence intervals using the Wilson method.

The percentage of days with wheezing within the first 2 years after the RSV infection will be presented descriptively by previous treatment group, including 95% CIs.

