Impact of the subject's health problems on the parent's/caregiver's health per Month	The extent to which the subject's health problems impacted the parent's/caregiver's health per Month. The answer to Questionnaire section E question 4.
Inability of the parent/caregiver to care for other family members due to the subject's health per Month	The inability of the parent/caregiver to care for other family members due to the subject's health per Month. The answer to Questionnaire section E question 5. The result will be either "Yes" or "No".
Subject's health limited the parent's/caregiver's time spent with other family members each Month	The extent to which the subject's health limited the parent's/caregiver's time spent with other family members each Month.

	The answer to Questionnaire section E question 6. The result will be categorical as listed in the Questionnaire.
Percentage of days other family members missed from work due to the subject's health problems per Month	The percentage of days each Month that other family members missed from work due to the subject's health problems. Derived base on the Questionnaire section E question 7. Calculated as the number of days as recorded in question 7 divided by the number of days since the last study visit/telephone call. For subjects currently not in paid employment, the value will be 100% for parents/caregivers who were not employed due to the child's health problem and missing if this was not due the child's health problem.
Clinical diagnosis of eczema within the first 2 years after the RSV infection	Clinical diagnosis of eczema within the first 2 years after the RSV infection, as diagnosed by a physician and reported by the parent/caregiver. The result will be either "Yes" or "No". Derived based on the answer to Questionnaire section C until the Month 24 analysis visit.
Clinical diagnosis of allergic rhinitis within the first 2 years after the RSV infection	Clinical diagnosis of allergic rhinitis within the first 2 years after the RSV infection, as diagnosed by a physician and reported by the parent/caregiver. The result will be either "Yes" or "No". Derived based on the answer to Questionnaire section D until the Month 24 analysis visit.

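### The primary asthma endpoint is limited to 2 years after RSV infection but is derived to the final visit, with no reference date and no check on the diagnosis date

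*SAP*

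**What the plan says.** **Asthma (primary).** SAP Section 5.1.3 reports "The proportions of subjects with clinical diagnosis of asthma within the first 2 years after the RSV infection" by previous treatment group, with Wilson intervals. The derivation in Section 5.1.1 is a single sentence: "This will be derived based on the completed study questionnaires at each visit/telephone call until the final visit".

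**Eczema and allergic rhinitis (exploratory).** SAP Section 5.3.1, Table 3, gives both the same 2-year window but a different stopping point. For eczema: "Derived based on the answer to Questionnaire section C until the Month 24 analysis visit". Allergic rhinitis has the parallel sentence for questionnaire Section D.

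**Visit clock in the protocol.** Section 9.1.3 has the questionnaire completed as follows: "At each study site visit (3, 6, 12, 18, and 24 months after entry visit"). Footnote a of the Time and Events Schedule says: "The entry visit needs to take place within 3 months after randomization in Study 64041575RSV2004". Section 9.1.2 adds: "The last visit of Study 64041575RSV2004 (ie, Day 28) may be combined with the entry visit of this LTFU study".

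**Visit clock in the SAP.** Section 1.2 places the site visits "at 3, 6, 12, 18, and 24 months after randomization in Study 64041575RSV2004".

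**Month labels.** SAP Section 2.1 uses the visit schedule held in the database and leaves a missing visit missing. SAP Section 2.5 bases the schedule on report entry dates, but calls the first report Screening and each later one the next month, starting at Month 2, and says that this reflects time since the RSV event.

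**Dates collected.** The questionnaire (Protocol Attachment 2) records the interview date and a full diagnosis date for asthma, eczema and allergic rhinitis. No SAP derivation uses the diagnosis dates.

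**The concern.** The endpoint is described by one time limit and derived with another. A programmer who follows the derivation counts every diagnosis reported up to the last visit. A programmer who wants to apply the 2-year limit has no date to count from: neither document defines the date of the RSV infection, and the SAP's only reference day is informed consent in this follow-up study (Sections 2.1 and 2.5).

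Two programmers could therefore classify the same child differently on a primary endpoint. In addition, three diagnosis endpoints with one stated window have two differently worded stopping points, and one of these rests on a label whose calendar meaning is not fixed.

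**Working it through.** The documents give no figure for this point, so there is none to reproduce. The check is date arithmetic.

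**Inputs**
- Entry visit: Day 28 after randomization at the earliest (Protocol Section 9.1.2), 3 months at the latest (Time and Events Schedule, footnote a).
- Final visit: 24 months after entry, ±7 days (Time and Events Schedule), or 24 months after randomization (SAP Section 1.2).
- Symptoms before randomization: up to 5 days, if the categories in SAP Section 4.1 cover everyone.
- Enrolled: 7 (SAP Section 2.4). The group split is not given.
- Assumptions: randomization stands in for the RSV infection date; one month = 365.25/12 = 30.44 days; 2 years = 730.5 days; 3 months = 91.3 days.

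**Step 1. Final visit on the protocol clock** = entry + 730.5 ± 7 days

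| Entry | Final visit (day) | With ±7 days | Days past 730.5 |
|---|---|---|---|
| Day 28 | 758.5 | 751.5 to 765.5 | 21 to 35 |
| 3 months | 821.8 | 814.8 to 828.8 | 84 to 98 |

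Every on-schedule completer is observed past 2 years, by 21 to 98 days. Counting from symptom onset adds at most 5 days, so the maximum is 103.

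**Step 2. Final visit on the SAP Section 1.2 clock** = 730.5 ± 7 days. The overrun is at most 7 days, or 12 from symptom onset.

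**Step 3. Where the Month 24 label falls.** The schedule has an entry visit, 5 site visits and "Monthly telephone calls between study site visits" in the other 24 − 5 = 19 months: 1 + 5 + 19 = 25 reports.

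*SAP Section 2.5 read literally.* The labels run Screening, Month 2, …, Month 25. Month 24 is the 24th report, 23 months after entry if none is missed:
- Day 28 entry: 28 + 23 × 30.44 = Day 728, about 2 days before the limit.
- 3-month entry: 91.3 + 23 × 30.44 = Day 791, about 61 days after it.

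With one report missed, the final visit itself becomes Month 24 (Day 758.5 or 821.8). With more missed, it carries a lower label and is still included.

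*Labels taken from the database, or from Protocol Section 10.1.* That section places completion at Month 24 of the assessment period. Month 24 is then the final visit. All three endpoints stop together, with the overrun of Step 1 on the protocol clock.

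**Step 4. Size.** For illustration, take groups of 2 and 5. One diagnosis changes the result as follows:
- n = 5: 0% (Wilson 0 to 43.4%) becomes 20% (3.6 to 62.4%).
- n = 2: 0% (0 to 65.8%) becomes 50% (9.5 to 90.5%).

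The documents give no 2-year asthma risk. As a rough order of magnitude only, borrow the 6.4% and 18.9% for recurrent wheezing in Protocol Section 1 and spread them evenly over 2 years. The expected number of late diagnoses is then 7 × 0.064 × 21/730.5 = 0.01 to 7 × 0.189 × 98/730.5 = 0.18. Those rates describe a different outcome in a different population.

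**The case against.** **The limit is written down.** It stands in the definition, the estimand (SAP Section 5.1.2) and the analysis method. The sentence on questionnaires can be read as naming the data source inside that limit. This is fair, so a reader who infers that asthma has no time limit at all goes too far. What remains is that the limit cannot be applied without a reference date, and that the stated rule does not apply it.

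**The SAP seems to treat follow-up as its 2-year window.** The other primary endpoint, the percentage of wheezing days, runs from consent to study completion, and the 2-year episode count in Table 2 runs from consent to the last trial day. This explains the wording, but on the protocol schedule it does not make the label accurate. It does mean that a cut-off for diagnoses alone would leave the two primary endpoints on different windows.

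**On the SAP's own clock the overrun nearly vanishes.** This is true. But Section 1.2 is a design summary that refers to the protocol for details, and the protocol uses the entry-visit clock in its synopsis, Time and Events Schedule and Section 9.1.3.

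**The month labels may be sound.** A reader might infer that the last report, as Month 25, counts for asthma but not for eczema or rhinitis, or that a missed report shifts all later months. Both need the literal reading of SAP Section 2.5. Against it stand SAP Section 2.1 and Tables 2 and 3, which take visits from the database, Section 2.5's own mention of entry dates, and Protocol Section 10.1. A mismatch is possible but not shown.

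**Listings would help.** Eczema and rhinitis diagnoses are listed by subject (SAP Section 5.3.2), as are all reportable adverse events (Section 6.1.2). A late case could probably be spotted, although no asthma listing is named.

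**Conclusion.** The point holds for asthma on the protocol schedule: the derivation can count diagnoses made about 21 to 98 days after the 2-year limit, because no reference date is named and the diagnosis date is not used. This rests on randomization as a stand-in for the infection date and on entry between Day 28 and 3 months. On the SAP Section 1.2 clock the excess is at most about 7 days, and the conflict between the clocks is itself a defect.

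For eczema and allergic rhinitis the finding is narrower. Their stopping point is ambiguous: it may equal the asthma stopping point, or it may vary with entry date and missed reports.

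The practical effect is small. Results are descriptive in 7 subjects, the extension was not pursued (SAP Section 3), and a late diagnosis is unlikely. Nothing here shows that any result is wrong; actual entry dates, missed reports and group sizes are not given. It is still worth correcting before analysis, because one case would visibly move a group proportion on a primary endpoint.

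**What to change.** - **Date limit.** Name one RSV reference date; randomization in the parent study is workable. Count asthma, eczema and allergic rhinitis as Yes only if the recorded diagnosis date is within 2 years of it. List later diagnoses separately and state a rule for incomplete dates.
- **Months.** Assign the analysis month from the interview date relative to one stated origin and leave missed months empty, or state that the database visit variable already does this. If the origin is the entry visit, remove the claim in SAP Section 2.5 that the labels reflect time since the RSV event.
- **Clock.** Reconcile SAP Section 1.2 with the protocol's entry-visit schedule.
- **Wheezing.** State that the percentage of wheezing days stays on the consent-to-completion window, or align it.

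**Cost.** The diagnosis and interview dates are already collected, and SAP Section 4.1 already inherits parent-study data timed to randomization, so the work is one date derivation and some wording. The real price is follow-up. The limit drops up to about 3 months, leaving 730.5 − 28 = 702.5 days of prospective observation after Day 28 entry and 730.5 − 91.3 = 639.2 days after 3-month entry, against 730.5 for every completer now. Observation time then depends on entry date. The early gap is not fully recovered, because recall at a later entry visit is limited to 30 days or less (Protocol Section 9.1.2). The SAP should say that this trade-off is accepted.

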- f. Medication use will be monitored throughout the study from signing of the informed consent form until the last study-related activity. Parents/caregivers will be required to bring all medications to the study site visit. Additionally, parents/caregivers will be required to document on a daily basis use of all medications on a medication parent/caregiver card, which will serve as a reminder card to be used during the study site visits and during the monthly phone calls between the study site visits for recording the medication used for respiratory infections and illnesses in the eCRF by the study site personnel. Parents/caregivers will be required to return the completed parent/caregiver cards to the study sites every 3 months (eg, in person or by mail/email/fax when no study site visit is scheduled).
- g. Collection of data on wheezing, asthma, eczema, allergic rhinitis, and impact of the subject's health status on normal daily activities for subjects, parents/caregivers, and other family members using a standardized questionnaire. The questionnaire should preferably be completed by the same study site responsible person, by

interviewing the subject's parent/caregiver. Parents/caregivers will complete the wheezing and medication parent/caregiver cards on a daily basis, which will aid the study site responsible person in completing the questionnaire during the interview. Parents/caregivers will be required to return the completed parent/caregiver cards to the study sites every 3 months (eg, in person or by mail/email/fax when no study site visit is scheduled).

- h. Once per calendar month ( $\pm 7$  days) from the entry visit.
- i. Data from lung function tests and allergy tests (immunoglobulin E and skin test), if available, will be collected as supporting documentation of the diagnosis of asthma, wheezing, and atopy as reported by the parent/caregiver.
- j. Medical resource utilization will be monitored throughout the study from signing of the informed consent form until the last study-related activity and will include medical visits, emergency room visits, and hospitalizations, all for respiratory conditions only and will be recorded in the eCRF. Visits with each type of health care provider (eg, general practitioner, pediatrician, physician assistant, nurse practitioner, pulmonologist, allergist, or other) will be specified in the eCRF.

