## **2.1.2. Endpoints**

### **Primary Endpoints**

The primary endpoints are:

- Clinical diagnosis of asthma within the first 2 years after the RSV infection, as diagnosed by a physician and reported by the parent/caregiver.  
All medical information needed to confirm the diagnosis of asthma needs to be collected by the study site personnel.
- Percentage of wheezing days within the first 2 years after the RSV infection, based on information reported by the parent/caregiver.

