**Protocol Number: 64041575RSV2002**

**Standardized Questionnaire for Use During Scheduled Study Site Visits and Monthly Phone Calls Between Study Site Visits**

### **General Instructions for the Study Site**

- The questionnaire needs to be completed in its entirety by the study site through parent/caregiver interviews during scheduled study site visits (entry visit, 3, 6, 12, 18, and 24 months) and monthly phone calls between study site visits.
- When referring to wheezing, eczema, and allergic rhinitis with the parent/caregiver, please use simple terminology provided in the definitions section (see below).
- Records need to be obtained from the subject's doctor or health care provider to confirm the diagnosis of asthma, eczema, and allergic rhinitis.
- Please keep completed questionnaires and wheezing/medication parent/caregiver cards as part of the study file.

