**Section B: Questions About Asthma**

**Important note for the study site: If on a previous questionnaire, the parent/caregiver indicated that the child has been diagnosed with asthma, please proceed to Section C.**

Please remind the parent/caregiver that the date of last interview was:

\_\_/\_\_/\_\_\_\_ (DD/MM/YYYY)

**1. Since the last study site visit/telephone call, has the child been diagnosed with asthma by a doctor or health care provider?**

No

Yes

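### The primary asthma endpoint is defined as a physician's diagnosis, but the SAP derives it from caregiver interviews alone and gives the confirming records no role

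*SAP*

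**What the plan says.** The endpoint definition in SAP 5.1.1 joins a physician's diagnosis to a caregiver's report. Its derivation rule follows: "This will be derived based on the completed study questionnaires at each visit/telephone call until the final visit". The result is Yes or No. SAP 5.1.3 presents the proportion by previous treatment group with Wilson 95% intervals, and SAP 5.1.2 frames the comparison as a difference in proportions.

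Protocol 2.1.2 has the same definition but adds a sentence that the SAP omits: "All medical information needed to confirm the diagnosis of asthma needs to be collected by the study site personnel". Protocol 9.1.2 and 9.1.3 repeat this for the entry visit and the follow-up interviews. The general instructions in Attachment 2 say that records must be obtained "to confirm the diagnosis of asthma, eczema, and allergic rhinitis".

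The interview item in Attachment 2, Section B, asks "has the child been diagnosed with asthma by a doctor or health care provider". If the answer is Yes, the form asks for the date. Once a Yes has been given, later interviews skip the section.

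Protocol 11.3.1 and the synopsis (Statistical Methods) describe both primary endpoints as reported by the caregiver.

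**The concern.** The definition names an event (a physician diagnosed asthma) and a route by which the study learns of it (the caregiver). The derivation uses only the route. A Yes given because a non-physician made the diagnosis, or one that the child's record does not support, would be counted as a physician-diagnosed case under the rule as written. The skip rule means that no later interview would revisit it.

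This is a primary endpoint, and the SAP reports only 7 subjects. The classification of a single child largely determines the estimate. A reader of the results could not tell whether a reported case meets the endpoint's own definition.

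**Working it through.** The plan states no expected asthma rate, power or event count, so there is no figure to reproduce. The check is a comparison of texts, followed by an illustration of size.

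**Step 1: definition and source.** SAP 5.1.1 puts the two side by side: "as diagnosed by a physician and reported by the parent/caregiver. This will be derived based on the completed study questionnaires". A physician's diagnosis is part of the definition, and the questionnaire is the only stated source.

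**Step 2: can the questionnaire show that a physician diagnosed?** Section B accepts a doctor or another provider. Footnote j of the Time and Events Schedule shows how widely the protocol uses the term: "each type of health care provider (eg, general practitioner, pediatrician, physician assistant, nurse practitioner, pulmonologist, allergist, or other". That list concerns resource-use visits, not who may diagnose asthma, so it shows usage only. The item's own wording already establishes the mismatch. The printed form has fields for Yes/No and a date, and none for the diagnoser or for confirmation. A Yes cannot separate a physician's diagnosis from another provider's.

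**Step 3: are the records used?** Attachment 2 requires them from the child's "doctor or health care provider to confirm the diagnosis of asthma, eczema, and allergic rhinitis". SAP 5.1, 5.3, 6 and 7 do not use these records, define a confirmed case, or say how an unconfirmed Yes is handled. SAP 5.3.2 names per-subject listings for eczema and allergic rhinitis diagnoses. SAP 5.2.2 lists derived efficacy parameters, which may include the asthma result. No listing of confirmation status is named.

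**Step 4: does the protocol give a rule?** It requires collection for confirmation, but does not say that a record changes Yes to No or what happens when none is found.

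**Step 5: size, as an illustration.** Inputs: n = 7 (SAP 2.4) and the Wilson 95% two-sided method (SAP 5.1.3), with z = 1.96 and z² = 3.8415. With p = x/n:

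- centre = (p + z²/2n) / (1 + z²/n)
- half-width = z·√(p(1−p)/n + z²/4n²) / (1 + z²/n)

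For 1/7: centre = (0.1429 + 0.2744)/1.5488 = 0.2694. Half-width = 1.96·√(0.01749 + 0.01960)/1.5488 = 0.2437. The interval is 2.6 to 51.3%.

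For 0/n the limits reduce to 0 and z²/(n + z²). For 0/7 the upper limit is 3.8415/10.8415 = 35.4%.

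The arm split is not given. The planned maximum of 120 to 60 is 2:1, and 7 × 2/3 = 4.7, so 5 and 2 is the nearest split. Arm sizes 2 to 5 are shown as an assumed range.

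| Denominator | Report counted | Report not counted | Shift (points) |
|---|---|---|---|
| 7 (all) | 14.3% (2.6 to 51.3) | 0% (0 to 35.4) | 14.3 |
| 5 | 20.0% (3.6 to 62.4) | 0% (0 to 43.4) | 20.0 |
| 4 | 25.0% (4.6 to 69.9) | 0% (0 to 49.0) | 25.0 |
| 3 | 33.3% (6.1 to 79.2) | 0% (0 to 56.1) | 33.3 |
| 2 | 50.0% (9.5 to 90.5) | 0% (0 to 65.8) | 50.0 |

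The difference in proportions in SAP 5.1.2 moves by the same amount as the arm concerned. A 6 to 1 split would give shifts of 16.7 and 100 points.

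**The case against.** A reader might infer that the SAP contradicts the protocol by discarding a required confirmation. The documents do not support that. Protocol 11.3.1 calls the endpoint caregiver-reported, and the confirmation sentence instructs sites to collect information rather than setting a classification rule. The SAP is silent on a point that the protocol left open.

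A reader might also infer that every caregiver Yes stands unchecked. That goes too far. Site staff complete the form by interview under instructions to obtain records. Protocol 17.5 allows queries and corrections, and 17.8 has monitors compare entries with medical records. A wrong Yes could be corrected this way. Still, neither document tells anyone to change a Yes when a record disagrees or is missing, so this route is possible but not planned.

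A third tempting step is to count a case only when a record shows a physician's diagnosis. That would narrow a caregiver-reported endpoint after the sample size is known. It would treat no record retrieved as no asthma, which can only lower incidence. Losing one true case in this way would cost the same 20 to 50 points in an arm of 5 down to 2. This objection stands and shapes the fix.

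It is also fair that the documents do not show that records were obtained, that they name the diagnoser, or that they reach the analysis database. The analysis is descriptive with no hypothesis test, so no error rate is affected.

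**Conclusion.** The point holds as a mismatch between definition and derivation that begins in the protocol and is carried into the SAP. Under the stated rule, a non-physician or unconfirmed report can be counted as a physician-diagnosed primary event, and the output would not show it.

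One such report is worth 14.3 points overall, or 20 to 50 points in an arm of 5 down to 2. This rests on three assumptions: the arm split, that at least one positive report exists, and that it is unconfirmed. The documents establish none of them, so they do not show that the estimate is wrong. What is affected is whether the estimate can be interpreted against its own definition. The change is worth making because it is small and any positive reports can be at most a handful.

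**What to change.** In SAP 5.1:

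- Keep the caregiver-reported incidence by previous treatment group, and label it as caregiver-reported.
- Add a row by group, with its Wilson interval, for cases whose collected record shows a physician's diagnosis.
- Show caregiver-reported cases without that confirmation in their own row, including any whose record shows only a non-physician's diagnosis.
- Add a per-subject asthma listing with the diagnosis date, the type of diagnoser if known, and confirmation status: confirmed, contradicted, or no record.
- State that a case with no retrievable record is not silently recoded to No.

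Apply the same layout to eczema and allergic rhinitis. SAP Table 3 also defines these as physician-diagnosed, the form items have the same broader wording, and sites must obtain records for them too.

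The cost is SAP wording, a short review of records for any positive reports, and the added rows and listing for each diagnosis. No new data collection is needed beyond what sites are already told to do.
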